17.2.2. Prior/Concomitant Medications/Procedures

Partially missing start/stop dates for prior/concomitant medications and partially missing start dates for prior/concomitant procedures will be imputed in the ADaM dataset for prior/concomitant medications/procedures.

- **Incomplete Start Date:**

Missing day and month

If the year is

- the same as the year of the first dosing date, then the day and month of the first dosing date will be assigned to the missing fields.
- prior to the year of first dosing date, then December 31 will be assigned to the missing fields.
- after the year of first dosing, then January 1 will be assigned to the missing fields.

Missing day only

- If the month and year are the same as the year and month of first dosing date, then the first dosing date will be assigned to the missing day.
- If either the year of the partial date is before the year of the first dosing date, or the year of the partial date and the first dosing date are the same but the month of partial date is before the month of the first dosing date, then the last day of the month will be assigned to the missing day.
- If either the year of the partial date is after the year of the first dosing date, or the years of the partial date and the first dosing date are the same but the month of partial date is after the month of the first dosing date, then the first day of the month will be assigned to the missing day.

CC-10004 (Apremilast)

Statistical Analysis Plan. Protocol CC-10004-PPP-001

- If the stop date is not missing, and the imputed start date is after the stop date, the start date will be imputed by the stop date.

Missing day, month, and year

- No imputation is needed.
- **Incomplete Stop Date:** If the imputed stop date is before the start date, then the imputed stop date will be equal to the start date.

Missing day and month

- If the year of the incomplete stop date is the same as the year of the last dosing date, then the day and month of the last dosing date will be assigned to the missing fields.
- If the year of the incomplete stop date is prior to the year of the last dosing date or prior to the year of the first dosing date, then December 31 will be assigned to the missing fields.
- If the year of the incomplete stop date is prior to the year of the last dosing date but is the same as the year of the first dosing date, then the first dosing date will be assigned to the missing date.
- If the year of the incomplete stop date is after the year of the last dosing date, then January 1st will be assigned to the missing fields.

Missing day only

- If the month and year of the incomplete stop date are the same as the month and year of the last dosing date, then the day of the last dosing date will be assigned to the missing day.
- If either the year of the partial date is not equal to the year of the last dosing date or the year of the partial date and the last dosing date are the same but the month of partial date is not equal to the month of the last dosing date, then that last day of the month will be assigned to the missing day.

17.2.3. Medical History

Partially missing medical history start dates will be imputed in the ADaM dataset for medical history (for the purposes of calculating durations of Palmoplantar Pustulosis). The 16th of the month will be used to impute a partially missing start date that has only the day missing, and July 1st will be used to impute a partially missing start date that has both the month and day missing. If the above imputation inappropriately results in a diagnosis date on or after the informed consent date, then the incomplete date will be assigned to the day prior to the informed consent date.

17.2.4. Treatment Duration

Partially or completely missing last dose dates will be imputed in the ADaM dataset for treatment duration.

CC-10004 (Apremilast)

Statistical Analysis Plan. Protocol CC-10004-PPP-001

When partially missing last dose date is available, set last dose date to the maximum of [the earliest possible date given the non-missing field(s) of last dose date, the minimum of (the latest possible date given the non-missing field(s) of last dose date, last known date in database, first non-missing discontinuation visit date)]

When last dose date is completely missing, set last dose date to the minimum of (last known date in database, first non-missing discontinuation visit date)

Last known date in database is defined as maximum of (last visit date, lab, vital signs, ECG assessment date, AE start or end dates, concomitant medications start or end dates, concomitant procedure date, last dose date from 'Disposition - Treatment' page, treatment exposure start or end dates where doses were completely or partially taken, death date).

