### **6.3.1. Observational Follow-up Visit**

Observational Follow-up evaluation will be performed on 28 days after last dose of IP. An administrative window of  $\pm$  7 days is permitted.

During the observational follow-up period;

- Subjects must complete all SROs prior to any other study procedure being performed.
- Efficacy assessments may be performed by the qualified physician who has completed the training for efficacy evaluation, but only after the subject has completed all SROs assessments.
- The physician performing efficacy assessments shall make independent observations at a given study visit and shall not review previous assessments in advance of conducting the assessments.

The following evaluations will be performed as specified in the Table of Events ([Table 5](#)):

- Concomitant medications and procedures evaluation
- AE/SAE evaluation (monitored through 28 days after the last dose of IP)
- Psychiatric evaluation
- Vital signs
- Weight
- Limited physical examination
- Clinical laboratory evaluations
  - Hematology/Chemistry
  - Immunology/Inflammation
- Efficacy assessment (see [Section 6.4](#))
  - PPPASI, PPSI, PGA and modified PPPASI
- Subject reported outcomes (see [Section 6.7](#))
  - Subject's VAS assessment for PPP symptom, Subject's assessment for PPP signs/findings

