9.1. Treatment Duration

Treatment duration will be descriptively summarized. Treatment duration (in weeks) is calculated as (the date of the last dose of IP – the date of the first dose of IP + 1) / 7. Imputation rule for partially or completely missing last dose date is specified in [Section 17.2.4](#). Summary statistics for treatment duration (in weeks), as well as a frequency summary of treatment duration categories (placebo-controlled phase: < 4, ≥ 4 to < 8, ≥ 8 to < 12, ≥ 12 to < 16, ≥ 16, active treatment phase: ≥ 16 to < 20, ≥ 20 to < 24, ≥ 24 to < 28, ≥ 28 to < 32, ≥ 32 weeks) will be provided.

Treatment duration for apremilast-exposure period is calculated from the date of the first apremilast administered, which is the date of the first administration of apremilast on/after the randomization at Week 0/Visit 2 or switched to apremilast at Week 16/Visit 10, to the last apremilast administered date for subjects who discontinue in the first 32 weeks or who complete the study at Week 32/Visit 14. Imputation rule for partially or completely missing last dose date is specified in [Section 17.2.4](#).

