- Exposure-adjusted incidence rate (EAIR) per 100 subject-years: The EAIR per 100 subject-years is defined as 100 times the number of subjects with the specific event divided by the total exposure time (in years) among subjects included in the analysis. Subjects with multiple occurrences of the specific event in the specific phase or analysis period will be counted only once in the numerator. The exposure time for a subject without the specific event is the treatment duration, whereas the exposure time for a subject with the specific event is the treatment duration up to the start date (inclusive) of the first occurrence of the specific event. The total exposure time in years is calculated by dividing the sum of exposure time in days over all subjects included in the analysis by 365.25. The EAIR per 100 subject-years is interpreted as the expected number of subjects with at least one occurrence of the specific event per 100 subject-years of exposure to IP.

For safety analysis, no inferential testing for statistical significance will be performed.

Individual subject listings will be provided for all safety data obtained.

As necessity requires, additional safety information may be provided.

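### SAP 17.2.4 can date a Week 32 completer's missing last dose at the follow-up visit, which adds about four weeks to that subject's exposure

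*SAP*

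**What the plan says.** SAP 9.1 computes treatment duration in weeks as ("the date of the last dose of IP – the date of the first dose of IP + 1) / 7" and sends partially or completely missing last dose dates to SAP 17.2.4. For the apremilast-exposure period it names both subjects who discontinue and those "or who complete the study at Week 32/Visit 14", so completers fall under the imputation rule.

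For a completely missing date, 17.2.4 reads: "When last dose date is completely missing, set last dose date to the minimum of (last known date in database, first non-missing discontinuation visit date"). It then states: "Last known date in database is defined as maximum of (last visit date, lab, vital signs, ECG assessment date, AE start or end dates", and the list goes on to concomitant medication and procedure dates, the last dose date on the Disposition – Treatment page, treatment exposure dates and the death date. Follow-up records are not excluded.

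For a partially missing date, the same two terms and the latest date compatible with the known fields go into a minimum. The result is then floored at the earliest compatible date.

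Protocol 6.3.1 sets the timing of the follow-up visit: "Observational Follow-up evaluation will be performed on 28 days after last dose of IP", with a window of ±7 days. Vital signs, weight, laboratory samples, AEs and medications are recorded there.

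**The concern.** The follow-up visit takes place off drug by design. Protocol Table 5 shows IP last dispensed at Week 28 and returned at Week 32. A rule that can place the last dose at the follow-up visit therefore assigns dosing to days when the subject should hold no tablets.

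Treatment duration is used in three places: the exposure tables (SAP 9), the denominators for TEAEs by exposure interval (SAP 11.1), and the exposure-adjusted incidence rate (EAIR). For the EAIR, SAP 11 states: "The exposure time for a subject without the specific event is the treatment duration". Off-drug time would enter that denominator and lower the rate. In the interval tables, a completer with exactly 32.0 weeks of exposure would be counted in the interval beyond 32 weeks.

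**Working it through.** The plan gives no figure for the effect of this imputation, so there is none to reproduce. The check follows the rule through for a completer and then does the date arithmetic.

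**Inputs**
- Day 1 first dose, Day 113 Week 16, Day 225 ± 4 for Visit 14: Protocol Table 5.
- Follow-up visit 28 ± 7 days after the last dose, so 21 to 35 days: Protocol 6.3.1.
- Duration = (last dose − first dose + 1)/7: SAP 9.1.
- 43 subjects per arm: Protocol 4.1.
- Assumptions: true last dose on Day 224, the day before the Week 32 target; first apremilast dose of switched subjects on Day 113.

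**Step 1: which date the rule returns.** SAP 5.2.1 ends the active treatment period either at Week 32/Visit 14 or on the day of discontinuation, as separate cases. On that reading a completer has no discontinuation visit date. The minimum then has one term left, the last known date, and with a Visit 15 record this is at least the Visit 15 date. An AE or medication date after Visit 15 would move it later still.

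**Step 2: error per affected completer**

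| | True | Imputed, +21 days | Imputed, +28 days | Imputed, +35 days |
|---|---|---|---|---|
| Apremilast from Week 0: (224 − 1 + 1)/7 | 32.0 weeks | 35.0 | 36.0 | 37.0 |
| Overstatement, of 224 days | | 21/224 = 9.4% | 28/224 = 12.5% | 35/224 = 15.6% |
| Switched at Week 16: (224 − 113 + 1)/7 | 16.0 weeks | 19.0 | 20.0 | 21.0 |
| Overstatement, of 112 days | | 21/112 = 18.8% | 28/112 = 25.0% | 35/112 = 31.3% |

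A true last dose on Day 225 changes the middle figures only to 12.4% and 24.8%.

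**Step 3: total apremilast exposure, if all 86 complete**
- Total: 43 × 224 + 43 × 112 = 9,632 + 4,816 = 14,448 days.
- One affected completer: 28/14,448 = 0.19%.
- An assumed 5% affected: 0.05 × 86 = 4.3 subjects; 4.3 × 28 = 120.4 days; 120.4/14,448 = 0.83%.
- For a rare event, where nearly everyone contributes full duration, an EAIR of 100 per 100 subject-years would become about 100/1.0083 = 99.2.

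**Step 4: partial dates.** With only the year known, the latest compatible date is 31 December. If the follow-up visit falls in that year, the inner minimum is again the last known date and the error is the same. With month and year known, the month end limits the date, so the error is usually smaller.

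**Step 5: with a cap at Visit 14.** For a last dose on Day 224 and Visit 14 on Day 221, 225 or 229, the errors are −3/7 = −0.43, +1/7 = +0.14 and +5/7 = +0.71 week. The completer's error falls from about 4 weeks to within about 0.7 week.

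**The case against.** The strongest reply is that the rule will rarely be triggered. It needs a subject who finished Week 32 and has no last dose date at all. The protocol requires dosing to be recorded in the eCRF (7.7.2), blister cards to be returned and counted (7.8), and a final count at Visit 14 (Table 5). SAP 17.1 says milestone dates should not be missing when the milestone occurs. This stands, and it keeps the point small.

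The second reply is that the SAP does not define the discontinuation visit. Protocol Table 5 labels the visit 14/ET, and Protocol 6.2.1 uses one end-of-treatment evaluation for completers and for those withdrawn. If that visit's date is the programmed variable, the error almost disappears. SAP 5.2.1 speaks against this reading but does not settle it, so the SAP needs to say which is meant.

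The third reply is that SAP 17.1 classes the study drug termination date as a milestone date and says milestone dates are not imputed. If that governs, there is no overstatement. But SAP 9.1 and 17.2.4 do impute the last dose date, so the sections conflict and the conflict needs resolving.

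A reader might infer that every affected completer lowers every EAIR. SAP 11 does not support that. A subject with the event contributes time only up to its first onset, so someone whose event began before the true last dose is unaffected in that event's rate.

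**Conclusion.** The rule is wrong as written for one narrow case: a Week 32 completer with a completely missing last dose date (or only the year known, with follow-up in that year), a follow-up record, and no date counted as a discontinuation visit. For that subject, exposure is overstated by about 4 weeks (3 to 5), which matters proportionately more in switched subjects.

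Two wider inferences are not supported:
- That missing last dose dates in general are imputed four weeks late. An early discontinuer with a discontinuation visit is held to that date by the minimum, and a completer with no record after Visit 14 is dated at about Visit 14.
- That the randomised safety comparison is biased. The error falls after Week 32, so Weeks 0–16 are untouched, and SAP 11 plans no inferential safety tests.

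The documents do not say how many completers will lack a last dose date. The aggregate of about 0.8% rests on an assumed 5% and on all 86 subjects completing. This is a minor point that should change no conclusion. It is worth correcting because the correction is almost free.

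**What to change.** Make these changes in SAP 17.2.4:

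1. Add the Visit 14/ET (end-of-treatment) visit date to the minimum, both in the rule for completely missing dates and in the inner minimum of the rule for partial dates. This also removes the dependence on how the discontinuation visit is defined.
2. Use a last dose date recorded on the Disposition – Treatment page first when one exists. At present it enters only through the maximum, so a later follow-up visit overrides it.
3. Reconcile 17.2.4 with SAP 17.1 by stating whether the last dose date is an exception to the rule that milestone dates are not imputed.

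AE and concomitant-medication dates need not be removed from the last known date. The cap is enough for completers, and removing those dates would change the rule for subjects lost to follow-up.

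The cost is two or three sentences and a small programming change. Subjects with a recorded last dose date are unaffected.
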